Using data from a Cochrane systematic review comparing surgical to non-surgical treatment for acute T ASD [6]; from the pooled results 3/58 patients in the surgical arm had subsequent further surgery (5.17%) compared to 17/61 in the non-surgical arm (27.9%) at a minimum follow up of 2-years (Risk Ratio 0.22, 95% CI 0.08 to 0.64). The large effect size is set in the context of the pooled results of 3 RCTs with uncertainty around the true size of the effect outside of a clinical trial setting in routine general practice. Conservatively, we would look to detect a smaller difference in subsequent surgery within 2-years of 25% in the non-surgical group, compared to 20% in the surgical group (an absolute difference of 5%). A 2-sided log rank test for equality of survival curves, with 90% power at 5% significance level (alpha), where outcome is time to re-dislocation, with an anticipated 25% re-dislocation rate in the non-surgical control group compared to a 20% in the surgical group (equivalent to a hazard ratio of 0.78), allowing for 10% loss to follow up and assuming equal group sizes, we require a total sample size of 3065 with 656 expected total of re-dislocations. There are 26,534 patients in CPRD with recurrent anterior shoulder dislocations, and at least 10,449 of these patients will be aged 16-35 years with T ASD [7]. The study will therefore be adequately powered. ***See flow diagram in appendix for estimation of numbers.***

H. Data Linkage Required (if applicable)

Data linkage and data management for our proposed study involves 2 different data sources (CPRD and HES). They need to be linked to answer the aims of WP2 as stated above. We have therefore included co-applicants with extensive experience in the use of linked datasets. The data management needed to produce a final working dataset will be carried out by a senior data manager at Oxford with expertise in such procedures. Under supervision from the application team, the data manager will develop ad-hoc code in Python and SQL to produce a dataset that can be analysed using standard statistical packages such as Stata.

I. Study Population

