The ***Intervention group*** will be patients in CPRD with first time T ASD who underwent shoulder stabilisation surgery after their first dislocation (early surgical repair in this NHS context will mean 'a decision to treat surgically after the first T ASD' and receiving surgery within 6 months). This means linking HES data to CPRD data in such a way that a HES surgical OPCS 4.7 code is seen to occur after a single first dislocation code in CPRD (without further dislocation codes) before that surgical date. The timelines between first dislocation codes and OPCS 4.7 codes will be recorded. The ***Control group***. While the most desirable control group would be physiotherapy, it is possible that WP1 will reveal that free text notes and referral codes on physiotherapy will be lacking and not reliable. If this is the case then conservative care will be defined as 'non surgical intervention' with no linked OPCS 4.7 surgical shoulder codes producing a control cohort of patients whose first time shoulder dislocation has been treated non-operatively. If however free text entries and referral codes for physiotherapy are reliably present in CPRD then conservative care will be physiotherapy identified by physiotherapy referral codes after a first time T ASD code. Any subsequent dislocation codes or OPCS 4.7 surgery code will be recorded.

K. Exposures, Outcomes and Covariates

As part of this application, we have performed a consensus survey of specialist shoulder surgeons and shoulder physiotherapists who are all members of the British Elbow and Shoulder Society. Saturation point and a list of predictors was reached rapidly and this list is tabulated in Appendix E and highlights the risk factors (and covariates) deemed most important. It is unlikely that all of these will be available from routinely collected national datasets but our study design will allow us to confirm through WP1 those factors that are reliably collected and that can be used for full analysis in WP2.

L. Data/ Statistical analysis

The association of surgical versus non-surgical intervention on subsequent re-dislocation within 2-years. The primary outcome of interest is the time from a first time traumatic anterior dislocation to subsequent re-dislocation within 2-years. The exposure of interest is whether or not a patient received shoulder surgery. In randomized controlled trials each person has

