Appendix C

The HES OPCS 4.7 codes that will be used are shown below. These codes have been provided to the lead applicant by the Expert Advisor in Orthopaedics to the Clinical Classifications Service HSCIC (Health and Social Care Information Centre) and Designated Centre for WHO FIC (Family of International Classifications Network). The codes are based on the following procedures “labral repair, stabilisation, capsular shift, Laterjet, bone transfer, SLAP repair and Bankart repair”. For any codes that do not define anatomical site, the following site codes should be present Z81.3 (Glenohumeral Joint) or Z81.4 (Shoulder Joint). The codes in *italics* are usually used for other joints such as the acromio-clavicular joint but we have been informed they are often used for shoulder stabilisation of the glenohumeral joint and will therefore need to be included in the analysis during linkage to CPRD shoulder dislocation codes.

HES OPCS 4.7 CODES.

Operative Description	OPCS 4.7 Codes
Stabilising operations on joint	W77
Repair of capsule of joint for stabilisation of joint NEC	W77.1
Transposition of muscle for stabilisation of joint	W77.2
Blocking operations on joint using prosthesis for stabilisation of joint	W77.3
Blocking operations on joint using bone for stabilisation of joint	W77.4
Periarticular osteotomy for stabilisation of joint	W77.5
Transposition of ligament for stabilisation of joint	W77.7
Other specified stabilising operations on joint	W77.8
Unspecified stabilising operations on joint	W77.9
Prosthetic replacement of ligament	W72
Primary prosthetic replacement of multiple ligaments	W72.1
Prosthetic replacement of multiple ligaments NEC	W72.2
Primary prosthetic replacement of intra-articular ligament	W72.3
Prosthetic replacement of intra-articular ligament NEC	W72.4
Primary prosthetic replacement of extra-articular ligament	W72.5
Prosthetic replacement of extra-articular ligament NEC	W72.6
Other specified prosthetic replacement of ligament	W72.8
Unspecified prosthetic replacement of ligament	W72.9
Other stabilising operations on joint	O27
Extra-articular ligament reconstruction for stabilisation of joint	O27.1

Repair of capsule and anterior and posterior labrum for stabilisation of glenohumeral joint	O27.2
Repair of capsule and anterior labrum for stabilisation of glenohumeral joint	O27.3
Repair of capsule and posterior labrum for stabilisation of glenohumeral joint	O27.4
Other reconstruction of ligament	W74

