3.	Do MRI or X-ray imaging reports confirm a diagnosis of traumatic dislocation by mentioning the presence of Hill Sachs, Bankart lesion, labral tear, labral detachment, dislocation, relocation, bony Bankart?	(If YES go to Q5)	(If NO go to Q4)

This project was funded by the National Institute for Health Research Health Technology Assessment (project number 14/160/01).

The views and opinions expressed therein are those of the authors and do not necessarily reflect those of the HTA, NIHR, NHS or the Department of Health.

4.	Do Hospital letters from specialists or physiotherapists confirm traumatic instability or traumatic shoulder dislocation?	(If YES go to Q5)	(If NO go to Q8)
5.	Is there any record of a dislocation prior to the CPRD first registration date at your practice?	(If YES go to Q6)	(If NO go to Q6)
6.	Are there any further dislocation codes in the record during the 2 years after the first dislocation code?	(If YES go to Q6b)	(If NO go to Q6c)
6b.	If YES is it clear (for each one) that this is a further dislocation episode rather than simply a review of the problem?	(If YES go to Q7)	(If NO go to Q7)
6c.	If NO, have there been any further dislocations recorded during the following 2 years that are not electronically coded?	(If YES go to Q7)	(If NO go to Q7)
7.	Are there any physiotherapy treatment codes for 2 years after the first dislocation code?	(If YES go to Q7b)	(If NO go to Q7c)
7b.	If YES is it clear that this physio code indicates the patient received physiotherapy for their shoulder?	(If YES go to Q8)	(If NO go to Q8)
7c.	If NO, is there any documentation that the patient has received physiotherapy for their shoulder without a code being entered?	(If YES go to Q8)	(If NO go to Q8)
8.	If your specific responses to this questionnaire indicate that this patient has not had a traumatic shoulder dislocation but your reading of the notes or your knowledge of the patient suggest they might have please tick the YES box, otherwise tick the NO box.	The end – thank you	The end – thank you

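### No rule ties the surgery or the re-dislocation to the shoulder that first dislocated, and the GP questionnaire does not ask the side, so other-shoulder events can dilute the hazard ratio by an unmeasured, probably modest, amount.

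*Protocol*

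**What the plan says.** - **Index event** (section F, main study): the first shoulder dislocation Read code in CPRD. None of the code descriptions in Appendix D carries a side, including the most frequent one (51,162 recorded events).
- **Intervention** (sections F and J): a listed OPCS 4.7 stabilisation code in HES, after one dislocation code with no further dislocation code before it, and within 6 months. For procedure codes that do not define the anatomical site, Appendix C adds that "the following site codes should be present Z81.3 (Glenohumeral Joint) or Z81.4 (Shoulder Joint". This names the joint, not left or right.
- **Outcome** (sections B and L): time to re-dislocation within 2 years, identified by CPRD codes. For the control group, section J says: "Any subsequent dislocation codes or OPCS 4.7 surgery code will be recorded".
- **Validation** (Appendix I): Q6b asks of later dislocation codes "If YES is it clear (for each one) that this is a further dislocation episode rather than simply a review of the problem". Q6c asks about later dislocations that were not coded. Neither asks which shoulder. The covering letter says the main phase depends wholly on electronic codes to find recurrences.
- **Stop/go** (section F): poor coding of first or recurrent dislocation in WP1 stops the study. The quantified threshold, a positive predictive value of at least 75%, is stated for patients with a first-time dislocation.
- **Planning figures** (section G): 2-year re-dislocation risks of 25% without surgery and 20% with it, given as a hazard ratio of 0.78, with 10% lost and two groups of the same size. The section's conclusion from these inputs is: "we require a total sample size of 3065 with 656 expected total of re-dislocations".

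**The concern.** Surgery treats one shoulder and can prevent recurrence only in that shoulder, yet every rule operates on the patient. Take a patient with a right dislocation, a right stabilisation and then a first left dislocation within 2 years. That patient carries a later dislocation code and is counted as a failure of surgery. A GP answering Q6b for that patient can truthfully tick YES, because it was a new episode and not a review.

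Two things are at stake. The hazard ratio for Aim 1, and the prediction model for Aim 2, would mix recurrence with a different event. And WP1, the one planned step at which someone reads the notes, would end without knowing how often this happens. A later analysis plan cannot recover a side that was not collected and that the code descriptions do not hold.

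**Working it through.** **1. The plan's own figures reproduce.** From the section G rates, HR = ln(0.80)/ln(0.75) = 0.776. With two-sided 5% significance and 90% power, (1.960 + 1.282)² = 10.507.
- Schoenfeld: 4 × 10.507 / (ln 0.776)² gives 652 events.
- Freedman: 10.507 × [(1 + 0.776)/(1 − 0.776)]² gives 659 events.

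The stated 656 lies between them. If the 10% loss is treated as exponential censoring over 2 years, the event probability is 0.2379 in controls and 0.1902 after surgery, mean 0.2140. Then 656/0.2140 = 3065. The sample-size arithmetic is sound.

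**2. Other-shoulder dislocations counted as outcomes.** Take 25% and 20% as same-shoulder risks and add an independent 2-year contralateral risk c, equal in both groups:

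p₀ = 1 − 0.75(1 − c), p₁ = 1 − 0.80(1 − c), HR = ln(1 − p₁)/ln(1 − p₀).

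Expected events are recomputed at N = 3065 with the same dropout model. Power = Φ(√events × (1 − HR)/(1 + HR) − 1.96). The values of c are **assumptions**.

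| c | p₀ | p₁ | HR | Events | Power |
|---|---|---|---|---|---|
| 0 | 25.00% | 20.00% | 0.7757 | 656 | 89.9% |
| 0.5% | 25.38% | 20.40% | 0.7795 | 667 | 89.3% |
| 1% | 25.75% | 20.80% | 0.7832 | 679 | 88.6% |
| 2% | 26.50% | 21.60% | 0.7904 | 701 | 87.3% |
| 3% | 27.25% | 22.40% | 0.7971 | 724 | 85.9% |

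If 25% and 20% are instead read as already including contralateral events, the planned power stands. The same-shoulder HR behind them would then be stronger than 0.776: 0.768 at c = 1% and 0.749 at c = 3%.

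**3. Other-shoulder surgery counted as the intervention.** Suppose a share m of the surgical group was operated on the other side and the index shoulder keeps the control risk (m also **assumed**): p₁ = (1 − m) × 20% + m × 25%.
- m = 2%: p₁ = 20.10%, HR 0.780, power 88.7%.
- m = 5%: p₁ = 20.25%, HR 0.787, power 86.6%.
- c = 2% and m = 5% together: HR 0.801, power 83.7%.

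**4. What WP1 can measure.** 100 questionnaires × 80% return × 25% recurrence ≈ 20 recurrences. If 2 of 20 were contralateral, the exact 95% interval for that share would run from about 1% to 32%.

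**The case against.** - **The word re-dislocation implies the same shoulder, and the letter tells GPs that true recurrences are being counted.** Many GPs may read Q6b that way. So a reader who infers that WP1 is bound to certify contralateral events as recurrences goes too far: the wording permits that answer but does not force it. The ambiguity itself stands.
- **The effect may be small.** Section D gives a male incidence of 34.9 per 100,000 person-years, about 0.07% over 2 years. Young people who have already dislocated once will exceed that, but even ten times the rate (0.7%) moves the HR only to about 0.781, with power near 89%. A reader might infer a fall in power toward 77% by supposing that 15% of control events are contralateral. Nothing in the documents supports that share, and the 77% also holds events at 656 although the extra dislocations would raise the count.
- **The intervention rule is narrower than any shoulder stabilisation.** A wrong-side operation must fall within 6 months, after one dislocation code and no second. This stands and limits the number, which is unknown.
- **Section G already plans conservatively**, with 25% against 20% where the pooled trials of further surgery gave a risk ratio of 0.22, and 3065 is a minimum. This softens the power point. It does not make the outcome the intended one.
- **Side matching could come later.** Appendix H is not visible, and an updated analysis plan follows WP1. But the protocol says the questionnaire follows Appendix H, the questionnaire itself is fully visible, and it does not ask the side.

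**Conclusion.** The point holds as a gap in the outcome and exposure definitions that WP1 could measure and, as written, does not. The expected direction is toward an HR of 1, provided contralateral risk is similar in the matched groups and unaffected by surgery; if it differs between them, the direction is not assured. The size cannot be taken from the documents and is probably modest: HR 0.776 to about 0.780–0.797, and power about 90% to 89–86%, for an assumed contralateral risk of 0.5% to 3%. Misassigned surgery would add to this.

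A reader might infer that the sample size is wrong or that the study cannot answer its question. Neither follows: 3065 and 656 reproduce, and the dilution is limited over the range shown. Nor would the side question alter the quantified 75% threshold, which is stated for first-time dislocation. It bears on the separate, unquantified judgement about recurrence coding.

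**What to change.** 1. Add to Q6b (for each later code) and Q6c: *Was this the same shoulder as the first dislocation?* Count a later code as a confirmed recurrence only if the answer is yes.
2. Report the contralateral share, with its confidence interval, in the stop-gap report to the funder.
3. With only about 20 recurrences expected, use that share to set the range of a WP2 sensitivity analysis of the HR, not to correct the HR numerically.
4. Where linked records give the side of both the index dislocation and the surgery, do not count surgery on the other side as the intervention.

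The cost is one tick-box per item on a form already being sent, plus one sensitivity analysis. The downside is that the confirmed predictive value of the recurrence codes may come out slightly lower.
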